### **3.4 Definition of Baseline values**

The study baseline value for a subject noted “Part A Baseline” will be defined as the latest measurement for that subject up to and including the day of administration of first study medication in Part A, unless otherwise stated. If a Part A Baseline measurement is missing or not collected, and a Screening value is available, the Screening value will be utilized as Part A Baseline instead. If no measurement is available prior to receiving study medication in Part A, the Part A Baseline value is treated as missing.

For subjects randomized into Part B, a “Part B Baseline” will be defined as the latest measurement for that subject up to and including the day of randomization, unless otherwise stated. If a Part B Baseline measurement is missing or not collected, and a post-Baseline Part A value is available, the post-Baseline Part A value will be utilized as Part B Baseline instead. If no post-Baseline Part A measurement is available prior to randomization, the Part B Baseline value is treated as missing.

For subjects experiencing a flare in Part B, a “Flare Baseline” will be defined as the latest measurement for that subject up to and including the day of administration of first escape treatment in Part B, unless otherwise stated. If a Flare Baseline measurement is missing or not collected, and a post-Baseline Part B value is available, the post-Baseline Part B value will be utilized as Flare Baseline instead. If no post-Baseline Part B measurement is available prior to receiving study medication in Escape Part, the Flare Baseline value is treated as missing. If a subject does not receive study medication in Escape Part, the last available post-Baseline Part B measurement will be used as Flare Baseline.

For each baseline definition, if there is evidence that measurements taken on the same day as administration of first study medication (in Part A/Part B) or first escape treatment (for subjects experiencing a flare in Part B) were actually taken after this administration, then only values strictly prior to that date (including screening assessment visits if appropriate) will be used for that subject. When the date of first dose is derived, it should be based on the first injection of study treatment, regardless of whether it is an active treatment.

Cases where the baseline value cannot be derived will be reviewed at the data evaluation meeting prior to database lock to determine an appropriate imputed value to use as substitute.

### **3.5 Protocol deviations**

Important protocol deviations will be predefined in the AS0005 Protocol Deviation Specification (PDS) document. Pre-analysis data evaluation meetings will be held prior to the Part A and Part B database locks.

The aim of the pre-analysis data reviews are to review the Data Management snapshot and draft and accept the list of protocol deviations which will then be used to determine exclusion from analysis sets as appropriate. These protocol deviations will be assessed as important by a panel including the clinical project manager, lead clinical development representative, study statistician, and other appropriate clinical study team members using the criteria pre-specified within the PDS document.

## **3.6 Analysis sets**

There will be 11 analysis sets used within this study.

### **3.6.1 Enrolled Set**

The Enrolled Set (ES) will consist of all subjects who have given informed consent.

### **3.6.2 Open-Label Set**

The Open-Label Set (OLS) will consist of all subjects who receive at least 1 dose of study medication in the Open-Label Period of the study (Part A).

### **3.6.3 Randomized Set**

The Randomized Set (RS) will consist of all subjects randomized into Part B of the study.

### **3.6.4 Safety Set**

The Safety Set (SS) will consist of all subjects in the ES who have received at least 1 dose of study medication.

### **3.6.5 Safety Set Part B**

The Safety Set Part B (SSB) will consist of all subjects in the RS who have received at least 1 dose of study medication in the Double-Blind Period of the study (Part B).

### **3.6.6 Full Analysis Set**

The Full Analysis Set (FAS) will be used to evaluate the sensitivity of the results of the primary efficacy analysis. The FAS will consist of all subjects in the RS who have received at least 1 dose of study medication in Part B, and have valid ASDAS measurements at Week 48 and at least 1 time point following Week 48.

### **3.6.7 Per Protocol Set**

The Per Protocol Set (PPS) will be used to evaluate the sensitivity of the results of the primary efficacy analysis. The PPS will consist of subjects in the FAS without any important protocol deviations that may influence the validity of the data for the primary efficacy variable.

### **3.6.8        Pharmacokinetic Set B**

The Pharmacokinetic Set B (PKSB) will consist of all subjects from the SSB who provide at least 1 PK sample during Part B.

### **3.6.9        Flared Set**

The Flared Set (FS) will consist of all subjects from the RS experiencing a flare in Part B. Since IXRS will be used to determine whether flare criteria (ASDAS>3.5 once or >2.1 on 2 consecutive visits, or ASDAS missing on 2 consecutive visits) are met during the course of the study, the population will be based on the IXRS data and whether they enter the Escape Part according to IXRS.

### **3.6.10       Escape Therapy Set**

The Escape Therapy Set (ETS) will consist of all subjects from the FS who have received at least 1 dose of escape therapy.

### **3.6.11       Part B Full-dose Set**

The Part B Full-Dose Set (FDS) will include all subjects from the RS who ever received a dose of CZP Q2W during Part B (including escape treatment).

### **3.6.12       General use of the Analysis Sets**

Efficacy summaries for variables collected in Part A will be based on the OLS. All efficacy analyses for Part B will be performed using the RS. The FAS and PPS will be used for a sensitivity analysis on the primary endpoint only. The other efficacy variables for subjects experiencing a flare in Part B will be based on the FS.

All safety summaries in Part A will be based on the SS. All safety summaries in Part B will be based on the SSB. The other safety variables for subjects experiencing a flare in Part B will be based on the ETS.

Pharmacokinetic and immunogenicity summaries will be based on PKSB.

## **3.7           Treatment assignment and treatment groups**

During Part A, all subjects will receive the same treatment consisting of 3 loading doses of CZP subcutaneous 400mg Q2W, followed by CZP 200mg Q2W. In the tabular summaries for Part A, all subjects will be summarized together, under a "All Subject" column. Summary tables may present subjects overall as well as broken out by axSpA subpopulation nr-axSpA and AS.

During Part B, subjects are expected to receive their treatment as randomized (PBO, CZP 200mg Q2W, CZP 200mg Q4W), unless escape treatment is required as a result of a flare. In the tabular summaries for Part B, subjects will be summarized according to their randomized or actual treatment group. Select summary tables will also present subjects broken out by axSpA subpopulation. In the tabular summaries for subjects experiencing a flare during Part B, subjects will be summarized according to their randomized treatment group; an overall column may also be included in select summary tables of safety data for these subjects.

Treatment assignments for the RS, FAS, PPS and FS will be according to randomization. Treatment assignments for the SSB, PKSB and ETS will be according to the actual treatment subjects received in Part B.

### 3.8 Center pooling strategy

Due to the small number of subjects expected at each center, centers will be pooled into regions (North America, Western Europe, Eastern Europe and Asia) for analysis purposes. The list of countries assigned to each region is provided in the table below.

**Table 3.4: List of countries in each region**

Region	List of countries
North America	USA
Western Europe	Belgium France Germany Netherlands Spain United Kingdom
Eastern Europe	Bulgaria Czech Republic Hungary Poland Romania
Asia	Turkey Taiwan

### 3.9 Coding dictionaries

Medical history and AEs will be recorded and coded using version 19.0 of the Medical Dictionary for Regulatory Activities (MedDRA®) criteria. Medications will be coded using the version from September 2015 of the World Health Organization Drug Dictionary (WHO-DD). Medical procedures will not be coded.

### 3.10 Changes to protocol-defined analyses

The SAP specifies which Baseline value is applicable for each analysis. The Flare Baseline is defined as the latest measurement for that subject up to and including the day of administration of first escape treatment in Part B instead of the visit in which the flare occurred.

In addition to the protocol, a modified version for ASDAS-MI is added for sensitivity analysis of ASDAS-MI.

Furthermore, analysis for IBD-Q response and IBD-Q remission using Part A Baseline and Part B Baseline as a reference and SF-36 PCS response and SF-36 MCS response using Part A Baseline as a reference are added.

Exploratory statistical comparisons for WPS will be based on MMRM instead of nonparametric bootstrap-t method.

ASDAS-Moderate Disease changed to ASDAS-Low Disease activity (Machado et al. 2018).  
LOCF analysis are removed from Part B efficacy tables.

MMRM will be used instead of ANCOVA based on LOCF for

- Total spinal pain
- Nocturnal spinal pain
- PtGADA
- Average of Questions 5 and 6 of the BASDAI concerning morning stiffness
- SF-36 PCS, MCS, and physical function domain
- Fatigue NRS
- ASQoL.

The primary purpose of the study is to evaluate treatment options of axSpA patients after being in sustained remission. Hence, one of the objectives is to evaluate the PK and immunogenicity of these patients. The CZP plasma concentration and ADAb titer of the patients that did not reach sustained remission are therefore not analysed, the Pharmacokinetic Set A (PKSA) as described in the protocol has been removed from the SAP.

## **4 STATISTICAL/ANALYTICAL ISSUES**

### **4.1 Adjustments for covariates**

The randomization stratification factors of geographical region and the mNY criteria as defined in Section 3.2.27 will be used as covariates in the specified statistical models. The original values of the stratification factors used at the time of randomization will be recorded into IXRS. Of note in case any errors to the stratification factors is detected, no updates will be done to the IXRS data. However, the correct values of the stratification factors (including any corrections post randomization) will be used for the analyses.

### **4.2 Handling of dropouts or missing data**

Post-flare efficacy data (except radiographic data) for subjects experiencing a flare (in any treatment group) will be treated as missing in Part B analyses. The pattern of missingness for these variables is assumed to be missing at random (MAR). For the summaries of data collected at post-flare visits in subjects experiencing a flare, there will be no adjustment for missing values and only observed case descriptive summaries will be provided.

For the primary efficacy variable (percentage of subjects in Part B who do not experience a flare), an approach based on the principles of NRI will be used to impute missing values. Specifically, if a subject withdraws from Part B at any point, they will be considered as having not responded to treatment. Therefore, they will be assumed to have experienced a flare during Part B for analysis purposes. Sensitivity analyses will be performed to assess the robustness of the results obtained using the NRI approach. Refer to Section 3.2.22 of this SAP for further details.

For the time to flare endpoint, the rules as described above for the primary endpoint will be applied to account for missing data when determining whether or not a subject experienced a

flare. Similarly, sensitivity analyses will also be performed to assess the robustness of the results obtained using the NRI approach. Refer to Section 3.2.23 of this SAP for further details.

For all analyses of binary endpoints (sustained remission, ASDAS-MI, ASDAS-CII, modified ASDAS-MI, ASAS20, ASAS40, ASAS5/6, ASAS PR, BASDAI50 response, IBD-Q remission, IBD-Q response, SF-36 PCS response, SF-36 MCS response) NRI will be used. Thus, unless mentioned otherwise (see Section 3.2.2 for ASAS20, ASAS40, ASAS5/6 and ASAS PR), a subject having missing data for the time point assessed will be conservatively counted as a non-responder. This will be done whether the data is missing, the subject discontinued prior to the time point assessed, or the data is considered missing due to start of escape treatment. For the following continuous endpoints in Part A, imputation of missing data will be performed using the LOCF approach:

- ASDAS
- BASDAI
- Fatigue item of BASDAI
- BASFI
- BASMI
- Nocturnal spinal pain score
- PtGADA
- CRP

In addition, ASDAS disease activity levels (ASDAS-ID, ASDAS-LD, ASDAS-HD and ASDAS-vHD) will be imputed based on the imputed values of ASDAS.

The LOCF imputation will be done whether the data is missing, the subject discontinued prior to the time point assessed, or the data is considered missing due to start of escape treatment.

Unless otherwise stated, the following guidelines apply for the LOCF analyses:

- For missing post-baseline Part A assessments, only carry forward earlier Part A post-Baseline values. Screening and Part A Baseline values do not get carried forward to the Part A post-Baseline visits.
- For missing post Week 48 Part B assessments,
  - if the subject did not experience a flare in Part B, only carry forward earlier Part B post-Week 48 values,
  - if the subject experienced a flare in Part B, the assessment at Escape week 0 will be treated as the last assessment in Part B prior to escape treatment. For any missing post 48 Part B assessments up to the week of flare (the later visit if flare was based on 2 visits), carry forward earlier Part B post-Week 48 values. Assessments whilst on escape treatment are not to be used, therefore the assessment at Escape week 0 will be carried forward for all subsequent visits until Week 96. E.g if the subject experienced a flare at week 72 then the Escape Week 0 assessment will be carried forward for the assessments after week 72 in Part B (76, 80, 84, 88, 92 and 96)

- Week 48 values do not get carried forward to the Part B post-Baseline visits.
- Assessments during escape treatment will not be carried forward.
- The following continuous endpoints in Part B will be compared between treatment groups using a mixed model for repeated measures (MMRM). The pattern of missingness for these variables is assumed to be MAR. Subjects who enter Part B will have already demonstrated sustained remission through 48 weeks on CZP 200mg Q2W. Many of these subjects will be randomized to receive placebo and will, therefore, be more likely to experience a flare. Post-flare data for subjects experiencing a flare (in any treatment group) will be treated as missing for the MMRM analysis. It is further assumed that most subjects who discontinue at this late stage in the study (i.e. during Part B) will do so as a result of reduced efficacy. Therefore, missing efficacy data due to either flare or study treatment discontinuation should be dependent on the observed efficacy scores, but independent of unobserved data. For the following continuous endpoints in Part B, imputation of missing data will be performed using the MMRM approach:
  - ASDAS
  - BASDAI
  - Average of Questions 5 and 6 of the BASDAI concerning morning stiffness
  - Fatigue item of BASDAI
  - BASFI
  - BASMI
  - Total spinal pain score
  - Nocturnal spinal pain score
  - ASQoL
  - PtGADA
  - SF-36 physical functioning score
  - SF-36 PCS
  - SF-36 MCS
  - WPS

The below rules will be applied for imputation of partial and missing start date of medications:

- If start day is missing, but month and year are present, start date will be replaced by the first day of the month of that year or by the day of start of study medication in Part A, if study medication in Part A was first administered in that month and year (exception: if in this case start date is after stop date, also the first day of the months will be utilized).
- If start day and month are missing and year is present, start date will be replaced by the first of January of that year or by the day and month of start of study medication in Part A, if study medication in Part A was first administered in that year (exception: if in this case start date is after stop date, also the first day of January will be utilized).

- If start day, month, and year are missing, start date will be replaced by the date of first study drug administration in Part A or by the first day of January of the year of the end date, if the first administration date is after the end date.

If medications are not ongoing (stopped) and the stop date is incomplete or missing, the following rules will be applied:

- If stop day is missing, but month and year are present, stop date will be replaced by the last day of the months or by the day of the last study drug administration in Part B if the last study drug administration in Part B occurs in that months and subject did not experience a flare. In subjects experiencing a flare in Part B and start escape therapy, stop date will be replaced by the last day of the months or by the day of the last administration of escape therapy if the last administration of escape therapy occurs in that month. For subjects not randomized into Part B, stop date will be replaced by the last day of the months or by the day of the last study drug administration in Part A if the last study drug administration in Part A occurs in that month. If in result of imputation, the stop date is before start date, also the last day of the months will be utilized.
- If stop day and months are missing and year is present, stop date will be replaced by last day of December or by the day and months of the last study drug administration in Part B if the last study drug administration in Part B was in that year and subject did not experience a flare. In subjects experiencing a flare in Part B and start escape therapy, stop date will be replaced by last day of December or by the day and months of the last administration of escape therapy if the last administration of escape therapy occurs in that year. For subjects not randomized into Part B, replacement by the day and months of the last study drug administration in Part A will be performed if the last study drug administration in Part A was in that year. If in result of imputation, the stop date is before start date, also the last day of December will be utilized.
- If stop day, months, and year are missing, stop date will be replaced by the date of the last visit in the double-blind period or by start date, if the last visit in the double-blind period date is before the start date.

The below rules will be applied for imputation of partial and missing AE start dates:

- If start day is missing, but month and year are present, start date will be replaced by the first day of the month of that year or by the day of start of study medication in Part A, if study medication in Part A was first administered in that month and year (exception: if in this case start date is after stop date, also the first day of the month will be utilized).
- If start day and month are missing and year is present, start date will be replaced by the first of January of that year or by the day and month of start of study medication in Part A, if study medication in Part A was first administered in that year (exception: if in this case start date is after stop date, also the first day of January will be utilized).
- If start day, month, and year are missing, start date will be replaced by the date of first study drug administration in Part A or by the first day of January of the year of the end date, if the first administration date is after the end date.

The below rules will be applied for imputation of partial and missing medical history start dates:

- If start day is missing, but month and year are present, start date will be replaced by the first day of the month of that year or by the day of start of study medication in Part A, if study medication in Part A was first administered in that month and year (exception: if in this case start date is after stop date, also the first day of the month will be utilized).
- If start day and month is missing for one item diagnosis (medical history of any of the preferred terms 'Axial Spondyloarthritis', 'Spondyloarthropathy', 'Ankylosing spondylitis' , or 'Spondylitis') or symptom (medical history preferred term of 'Back pain', 'Inflammatory pain', 'Spinal Pain', 'Lumbar spine pain') and the year is similar, the missing month will be imputed by the month of the other item.
- If only one item diagnosis or symptom is present and if start day and month are missing and year is present, start date will be replaced by the first of January of that year or by the day and month of start of study medication in Part A, if study medication in Part A was first administered in that year (exception: if in this case start date is after stop date, also the first day of January will be utilized).
- If start day, month, and year are missing, start date will be replaced by the date of first study drug administration in Part A or by the first day of January of the year of the end date, if the first administration date is after the end date.

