### **3.2.17 Resource utilization**

The following resource utilization data will be collected through UCB standardized modules:

- Concomitant medical procedures
- Health care provider consultations not foreseen by the protocol
- In-patient hospitalizations and emergency room visits (including length of stay)

A medical resource will be allocated to Part A as determined by the (start) date of the event.

Specifically, a medical resource will be allocated to Part A if (start) date is on or after the date of first study medication in Part A and prior to or on the date of last study medication in Part A + 70 days and prior to the date of first study medication in Part B, if any.

A medical resource will be allocated to Part B as determined by the (start) date of the event.

Specifically, a medical resource will be allocated to Part B if (start) date is on or after the date of first study medication in Part B and prior to or on the date of last study medication in Part B + 70 days. Medical resource with a (start) date after date of first escape full-dose CZP injection will be excluded from any summary tables of medical resource in Part B.

A medical resource will be allocated to Part B post-flare as determined by the (start) date of the event. Specifically, a medical resource will be allocated to Part B post-flare if (start) date is on or after the date of first escape full-dose CZP injection in Part B and prior to or on the date of last escape full-dose CZP injection in Part B + 70 days.

The same rules for (partially) missing start dates as for AEs will be applied to the resource use data.

For the same subject only one hospitalization will be considered if “start date of the second hospitalization - end date of the first hospitalization  $\leq 1$ ”.

In case of complete consultation date, count only once for a same subject, same consultation date, same location and same provider.

If the procedure name, start date and relationship are the same, then only one procedure is counted, otherwise if at least one variable among procedure name, start date or relationship is different, distinct/several procedures are counted.

If concomitant medical procedures, health care provider consultations not foreseen by the protocol, and in-patient hospitalizations and emergency room visits are not available during Part A, Part B and Part B post-flare the respective number variable will be set to 0.

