### Treatment-Emergent AEs (TEAEs)

Treatment emergent AEs (TEAEs) will be defined and summarized in four different ways:

[1] TEAEs in Part A: will be defined as all AEs starting on or after the date of first study medication in Part A and up to 70 days after the last dose of study medication in Part A and before the date of the first study medication in Part B if any.

[2] TEAEs in Part B prior to flare: will be defined as all AEs starting on or after the date of first study medication in Part B and up to 70 days after the last dose of study medication in Part B. AEs occurring more than 70 days after the last dose in Part B will not be considered treatment emergent, regardless of whether this occurs during the SFU period, or after a treatment gap of more than 70 days. AEs which emerge post-flare will be excluded from any summary tables of TEAEs in Part B prior to flare.

[3] TEAEs in Part B in subjects experiencing a flare: Pre-flare TEAEs in Part B will be defined as any TEAEs in Part B with an onset date before the start date of escape therapy. Post-flare TEAEs in Part B will be defined as any TEAEs in Part B with an onset date on or after the start date of escape therapy.

[4] TEAEs in Part B under CZP full-dose therapy: These will be defined for subjects in the FDS who ever received a dose of CZP 200mg Q2W during Part B as double-blind or as escape treatment.

TEAEs in Part B under CZP full-dose therapy will be defined as follows:

- In subjects randomized into Part B to the PBO or CZP 200mg Q4W arm who do experience a flare and do escape to CZP full-dose therapy, TEAEs under CZP full-dose therapy will include all post-flare TEAEs in Part B
- In subjects randomized into Part B to CZP 200mg Q2W arm, TEAEs under CZP full-dose therapy will include all TEAEs in Part B

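### Incomplete AE start dates are anchored only to the first Part A dose, so some Part B events are counted in Part A and some events on escape treatment are counted as pre-flare

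*SAP*

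**What the plan says.** SAP Section 4.2 has three rules for incomplete AE start dates.

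- **Day missing:** "start date will be replaced by the first day of the month of that year or by the day of start of study medication". The second option means the first Part A dose and applies if that dose fell in the same month and year.
- **Day and month missing:** "start date will be replaced by the first of January of that year or by the day and month of start of study medication". Again the second option means the first Part A dose and applies if that dose fell in the same year.
- **Everything missing:** "start date will be replaced by the date of first study drug administration in Part A". The fallback, where that dose came after the AE ended, is 1 January of the end-date year.

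The data handling rules for AEs in Section 10.2 add nothing on dates.

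Section 10.2 then sorts events by start date. Part A events must start within the Part A window "and before the date of the first study medication in Part B if any". Part B events are "all AEs starting on or after the date of first study medication in Part B"; within Part B the start of escape therapy separates pre-flare from post-flare. The AE tables are produced separately for these groups, with exposure-adjusted rates for all TEAEs and serious TEAEs. Section 3.2.17 carries the rule further: "The same rules for (partially) missing start dates as for AEs will be applied to the resource use data".

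**The concern.** The safety analysis has two period boundaries after the first Part A dose: the first Part B dose and the first escape dose. The imputation rule recognises neither. Every fallback date is at or before the true onset, or is the Part A start, so an error at either boundary puts the event in an earlier period.

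The two boundaries differ in effect. At the Part A/Part B boundary, events leave all three randomized arms. At the escape boundary, an event that began on full-dose CZP given as escape is put in the pre-flare table under the treatment received in Part B (Section 3.7). Time at risk in that table is censored at the first escape dose (Section 10.1.2.1), so the numerator gains an event without the matching exposure. For placebo and half-dose subjects the same event leaves the Part B full-dose table, which counts only their post-flare events. Both effects make CZP look relatively safer.

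This looks like an oversight: in the same section, the stop-date rules for medications do distinguish Part A, Part B and escape.

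**Working it through.** **The rule applied to one subject.** Illustrative dates: Part A starts 17 Mar 2016; Part B starts 336 days later, 16 Feb 2017; escape starts 26 weeks after that, 17 Aug 2017.

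| True onset (period) | Day missing | Year only | Fully missing |
|---|---|---|---|
| 21 Feb 2017 (Part B) | 1 Feb 2017: Part A | 1 Jan 2017: Part A | 17 Mar 2016: Part A |
| 20 Aug 2017 (escape) | 1 Aug 2017: pre-flare | 1 Jan 2017: Part A | 17 Mar 2016: Part A |
| 26 Sep 2017 (escape) | 1 Sep 2017: post-flare, correct | 1 Jan 2017: Part A | 17 Mar 2016: Part A |

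A day-missing date therefore fails only in the calendar month of a boundary dose. It is unaffected if that dose fell on the first of the month. If Part B and escape began in the same month, a day-missing escape event goes to Part A instead.

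**Part B events sent to Part A.** Assumptions, not in the SAP: Part B starts are uniform over the calendar year and onsets are uniform over Part B. Part B lasts L = 48/52.18 = 0.92 year, or 0.92 × 12 = 11.04 months.

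- Day missing: on average half a month of the boundary month remains, so 0.5/11.04 = 4.5%.
- Year only: with start u uniform on (0,1), the share is the mean of min(L, 1−u)/L = 1 − L/2 = 1 − 0.46 = 54%.
- Fully missing: 100%, unless the AE ended before the first Part A dose.

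A simulation of the literal rules, 50,000 events per scenario, gave 4.4%, 54% and 100%.

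**Escape events.** Here the share depends on how long escape lasts. Half a month is about 15.2 days, so for day-missing dates the approximation is 15.2/84 = 18%, 15.2/168 = 9% and 15.2/252 = 6%. Simulation, with escape running to the end of Part B:

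| Escape length | Day missing, to pre-flare | Year only, to pre-flare | Year only, to Part A | Fully missing, to Part A |
|---|---|---|---|---|
| 84 days | 17.6% | 69% | 19% | 100% |
| 168 days | 8.6% | 46% | 31% | 100% |
| 252 days | 5.9% | 23% | 42% | 100% |

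**Which arms.** Section 2.4 assumes no-flare rates of 80% (full dose), 75% (half dose) and 45% (placebo) with 70 per arm. As a check that these inputs are read correctly, continuity-corrected power is 98.9% and 94.1%, against the stated 98% and 94%. Expected flares are 70 × 0.20 = 14, 70 × 0.25 = 17.5 and 70 × 0.55 = 38.5, which total 70. Placebo supplies 38.5/70 = 55% of flares, and 38.5/(38.5 + 17.5) = 69% of flares in subjects whose assigned regimen changes at escape.

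**The case against.** The strongest reply is that the practical effect may be trivial. The SAP does not say how many AE dates are incomplete. Part B time points are two weeks apart, so a year-only date should be rare, and day-missing dates fail only in a boundary month. AE summaries are descriptive, no efficacy result is touched, and AE data are listed with relative day left blank for partial dates, so affected events can be found. All of this stands, and it limits the point to a specification gap.

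A second reply is that a later anchor has a mirror error. By the same arithmetic, the mean of min(L, u)/L = 1 − L/2 = 54% of true Part A AEs in randomized subjects fall in the calendar year of the first Part B dose. Moving every year-only date forward would push open-label CZP events into randomized columns, placebo included. This is right, and it is why later anchors should be confined to month-known dates, where the mirror error is about 4.5%.

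Three stronger readings are tempting but unsupported:

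- **Every Part B and escape safety table is biased in favour of CZP.** Laboratory and vital-sign tables are visit-based and unaffected. For subjects randomized to full dose, the Part B full-dose table does not change with a pre-/post-flare shift, and the study-wide full-dose summary changes under neither shift. The pre-flare table gains events as well as losing them.
- **All escape AEs with incomplete dates land in the placebo column.** Fully missing dates go to Part A, year-only dates can go to either period, and half-dose and full-dose escapers return to their own columns.
- **The 55% and 20% are escape rates.** They are complements of the no-flare assumptions, and Section 3.2.22 counts any premature withdrawal as a flare. Withdrawn subjects need not receive escape treatment.

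**Conclusion.** The gap is real and narrow. As written, a day-missing AE in the month of the first Part B dose is counted in Part A, and one in the month of the first escape dose is counted before escape, with the first-of-month and same-month exceptions noted. Year-only dates can move back one or two periods, and fully missing dates go to Part A unless the AE ended before the first Part A dose.

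The shares of affected dates are about 4.5% (day missing) and 54% (year only) at the Part B boundary. For day-missing escape events the share moved to pre-flare is about 6% to 18%. All rest on uniform entry and onset, and the escape figures also on its duration. The number of events cannot be stated. The direction at the escape boundary is clear: events that began on escape CZP enter the pre-flare numerator without exposure, and placebo is the likeliest arm, although its 55% share of flares is a planning figure that includes withdrawals. The rule should be amended, because with about 70 subjects per arm a few misplaced serious events could be visible.

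**What to change.** Amend the AE start-date rules in Section 4.2:

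1. **Month and year known.** If the month is that of the first escape dose, impute the escape start date. Otherwise, if it is that of the first Part B dose, impute that date. Otherwise keep the present rule. Never impute after a known stop date.
2. **Year only or fully missing.** Use the known stop date to rule out periods that are not possible, and state which of the remaining periods is used. A stop date is only an upper bound: it can exclude later periods but cannot exclude Part A.
3. **Report** the number of AEs whose period rests on an imputed date, with a sensitivity count under the alternative (earlier-period) assignment.
4. Apply the same rules to resource use (Section 3.2.17).

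The cost is a few lines of text and code and one extra count, best settled before unblinding. The drawback is that some events that truly began earlier in a boundary month move forward. At the escape boundary this counts against CZP. At the Part B boundary it moves some open-label CZP events into the randomized columns, placebo included. The sensitivity count shows how many events are involved.
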